Gait Training Combined With Behavioral Strategies for People
With Stroke

Study Protocol & Statistical Analysis Plan

NCT 04546217

October 19th, 2020

[name], PhD, OTD, Principal Investigator
University of Alabama at Birmingham
[name]

1. Study Protocol

Although a variety of strategies to improve motor function of the paretic lower extremity after stroke have been developed in the past two decades, there is still no consensus on the best intervention to improve walking and mobility impairments. One of the most common interventions to address walking after stroke is treadmill training with and without body weight support (BWS). These modalities have produced significant improvements in walking speed and endurance during and immediately after the intervention. Yet, motor function improvements are not maintained on follow-up assessments and there is no clear evidence of how well improvements transfer to everyday situations.

While the above strategies focus on step repetition and increased exercise intensity, strategies focusing on behavior management in rehabilitation protocols could promote long-term recovery of function by encouraging participation in activities outside clinical settings or research protocols. In fact, the combination of motor training with behavior management strategies has been shown to be an effective mechanism to produce long-lasting improvements in motor function in real life situations in people with stroke. However, few studies using behavior management strategies for lower extremity (LE) function for people with stroke have been published. Preliminary studies on the effectiveness of motor training combined with behavior management strategies showed significant improvement in real-world use of the paretic LE. In these studies, the systematic and structured application of a group of strategies called the Transfer Package (TP) was associated with the lasting effects.

This study aimed to investigate the effect of BWS gait training in a robotic treadmill with the TP on (1) changes on walking speed, endurance, motor function and use of the affected LE, and (2) long-term retention of improvement on these outcomes.

This study was approved by the Institution Review Board (IRB) at the University of Alabama at Birmingham (IRB-300005407-006). All participants signed an informed consent form prior to their inclusion in this study. Nineteen individuals in the chronic phase of recovery after stroke were included in this parallel pilot randomized trial of a robotic treadmill gait protocol combined with behavior management strategies.

All participants received a 6-week intervention that consists of 30–60 minutes of Treadmill Training (TT) sessions, depending on the individual's endurance. The experimental group also received a group of behavioral strategies called the “transfer package” (TP) for 30 minutes after each training session. On the first day of the intervention, the control group (TT) received a handbook with exercises and stretching techniques suggested by the American Stroke Association (ASA). Participants were assessed immediately before and after the intervention, as well as 3 and 6 months after the intervention. All participants received the same TT, which consisted of 18 sessions distributed over 6 weeks (Figure 1). The TT sessions were divided into endurance, strength, and walking speed training, with six sessions for each of these modalities (Figure 1).

[figure not shown]
Figure 1. Modalities of Treadmill Training

The intervention group (TT+TP) received the TT combined with the TP (Figure 2). The original TP is an element of the well-established Constraint-induced Movement Therapy. Participants were asked to sign the behavioral contract (BC). The purpose of the BC is to

ensure that participants: (1) perform tasks with the affected LE in a safe manner, (2) increase use of the more-affected LE in daily tasks, and (3) increase coordination between both LEs. Additionally, the behavioral contract formally engages the patient in actively exploring more ways to use their more-affected LE outside the clinical setting and in adopting a problem-solving approach to accomplish that end.

Figure 2. Combined intervention model

During the 6-week intervention and after every TT session, a new HSA was developed. Each list included up to 10 tasks or exercises to be performed daily between the TT sessions. The list was reviewed at the next session by the therapist, to check: 1) if all activities were performed and 2) if there was any challenge in the participant's performance that should be addressed (e.g., level of difficulty of the task and safety).

The use of the affected limb was assessed in all treatment sessions through the administration of the LE-MAL. A full description of the LE-MAL is provided in the outcomes section.

The last component of the TP is the Home Practice (HP), which is a list of exercises that the participant should do daily after the end of the treatment period. This list was given to the participant at the end of the last day of the intervention. The purpose of the HP is to assure continued progress with LE use after the intervention program is completed. The expectation was that engagement in home practice would help individuals maintain the changes observed due to the intervention.

The control group (TT) received the same treadmill training described above and also received a list of exercises at the beginning of the intervention (i.e., session 1). The handouts were based on videos provided by the American Stroke Association (available at <https://www.stroke.org/en/life-after-stroke/stroke-rehab/post-stroke-exercise-videos>). All participants received the same list of exercises.

2. Statistical Analysis Plan

An initial sample of 24 individuals would be selected for this pilot trial. However, due to time and recruitment constraints faced by the PI during the SARS-COVID pandemic, this sample size dropped. A total of 19 people with chronic stroke were selected and were randomly allocated using a 2:1 ratio to either TT+TP (N = 12) or TT group (N=7). Individuals were allocated using an online randomization tool (randomization.com, first generator).

The primary outcomes were the Lower Extremity Motor Activity Log (LE-MAL), Berg Balance Scale (BBS), 10 Meter Walking Test (10MWT), and 6-minute walking test (6MWT). The secondary outcomes were: 5 times sit to stand (5TSTS), and the Fear of Falling Avoidance Behavior Questionnaire (FFABQ).

Assessments were administered pre- and post-treatment, and at follow-up visits (3 and 6 months after the end of the intervention protocol). Each assessment visit lasted approximately 60 minutes and was conducted by a physical therapist blinded to group assignment.

Demographic characteristics including age, gender assigned at birth, chronicity, ethnicity, race, and NeuroQoL score were reported by frequency (%) mean and standard deviation, or range. Due to the small sample size, a descriptive analysis was conducted, and results are shown in mean scores and standard deviation in each time point. The average scores at post-treatment, 3 months follow up and 6 month follow up visit were compared to the average scores obtained at pre-treatment. The differences were compared to the Minimal Clinically Importance Difference (MCID), or Minimal Detectable Change (MDC) of each outcome, if reported in the literature, to identify

significant changes since statistical analysis was not conducted due to the small sample size.

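### The aim is worded as the effect of robotic gait training with the TP, but both arms train; randomisation identifies only what the TP package adds, and the analysis plan states no between-arm contrast to estimate it

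*Combined protocol and SAP*

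**What the plan says.** All references are to the combined protocol and SAP.

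- **Aim (Section 1, end of the introduction).** "This study aimed to investigate the effect of BWS gait training in a robotic treadmill with the TP", on walking speed, endurance, motor function and use of the affected leg, and on long-term retention of improvement. No comparator is named for either part.
- **Common treatment (Section 1).** "All participants received the same TT, which consisted of 18 sessions distributed over 6 weeks". Session length is given as "30–60 minutes of Treadmill Training (TT) sessions, depending on the individual's endurance".
- **Experimental arm only (Section 1).** "The experimental group also received a group of behavioral strategies called the “transfer package” (TP) for 30 minutes after each training session". A new task list followed every session: "Each list included up to 10 tasks or exercises to be performed daily between the TT sessions". On checking of these tasks, the text states: "The list was reviewed at the next session by the therapist". On the last day a home-practice list was issued for daily use after treatment; the document counts this as a component of the TP.
- **Control arm (Section 1).** "On the first day of the intervention, the control group (TT) received a handbook with exercises and stretching techniques". The material was given once, at session 1. No frequency of use and no review are described.
- **Analysis (Section 2).** Means and standard deviations are shown at each time point. Post-treatment, 3-month and 6-month means are compared with pre-treatment means, and the differences are judged against MCID or MDC values from the literature. No statistical testing and no between-arm comparison are stated.
- **Size (Section 2).** 19 participants were allocated, 12 to TT+TP and 7 to TT.

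**The concern.** The aim, the randomised comparison and the analysis point at three different quantities. The aim, read literally, asks for the effect of treadmill training and TP together. The randomisation compares TT+TP with TT plus a handout, which is an add-on question. The analysis looks at change from baseline, which is neither.

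A TT+TP mean that improves by more than an MCID would, under the aim as worded, be presented as the effect of gait training with the TP. That change also contains everything that would have happened without the TP: the treadmill training itself, retest familiarity, regression to the mean and time. The one comparison protected by randomisation would not be reported as an estimate.

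The retention aim has the same difficulty. At 3 and 6 months the TT+TP arm has a daily home-practice list as part of its assigned package, while no end-of-treatment list is described for controls. A comparison at those visits concerns the package including home practice, and the aim does not say so.

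**Working it through.** **1. What each comparison contains.** Write the mean change from pre-treatment as a sum of parts: *b* for everything unrelated to treatment (time, retest, regression to the mean), *t* for treadmill training, *p* for the TP package given on top of TT, and *h* for the handout given on top of TT.

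- Change in TT+TP = *b* + *t* + *p*
- Change in TT = *b* + *t* + *h*
- Between-arm difference in change = *p* − *h*

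The literal aim is *t* + *p*. Obtaining it needs *b*, and no arm goes without treadmill training, so *b* cannot be separated from *t*. The within-arm change differs from the aim by *b*, whose size is unknown. Exceeding an MCID or MDC does not remove *b*. The randomised contrast removes both *b* and *t* and leaves the package over the handout. If the handout list also went to TT+TP (see the objection), *h* drops out and the contrast is *p*.

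**2. Scheduled session time.** The document gives no total, so there is no stated figure to reproduce. Inputs from Section 1: 18 sessions, TT of 30 to 60 min per session, and TP "for 30 minutes after each training session".

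| Quantity | Shortest TT sessions | Longest TT sessions |
|---|---|---|
| TT hours, each arm | 18 x 30 / 60 = 9 h | 18 x 60 / 60 = 18 h |
| TP hours, TT+TP only | 18 x 30 / 60 = 9 h | 9 h |
| Total, TT+TP | 9 + 9 = 18 h | 18 + 9 = 27 h |
| Total, TT | 9 h | 18 h |
| Ratio TT+TP : TT | 18 / 9 = 2.0 | 27 / 18 = 1.5 |

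The ratios assume equal TT session length in the two arms and that all 18 TP sessions were given. Home tasks come on top and cannot be put into hours from the document.

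**3. Precision of the contrast that should be reported.** With 12 and 7 participants, complete data and a common standard deviation of change SD, the standard error is SD x √(1/12 + 1/7) = SD x √0.2262 = 0.476 SD. With 12 + 7 − 2 = 17 degrees of freedom the two-sided 95% t multiplier is 2.11, so the half-width is 2.11 x 0.476 = about 1.0 SD. The interval is wide and gets wider with loss to follow-up. The 95% level is an assumption; the plan sets none.

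**The case against.** The strongest reply is that the design is coherent as an add-on trial. The rationale in Section 1 is that treadmill gains fade and that behavioural strategies may make them last. Randomising TT+TP against TT plus a handout addresses that directly, and gait training with the TP can reasonably be read as the experimental regimen, to be set against the stated control. This stands. A reader might infer that the design answers no useful question; the document does not support that, because the add-on question is the one the randomisation targets.

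A second reply concerns the extra time and daily practice. A reader might infer that these confound the TP and that the trial claims an effect of behavioural strategy by itself. Neither is supported. Section 1 presents activity outside the clinic as the means by which such strategies work, places the lists within the TT+TP programme and calls home practice part of the TP. Assigned and reviewed practice is therefore intervention content, and nowhere does the document say a difference would be credited to behavioural strategy alone. What remains is that session time was not matched, so the conclusion should stay with the whole package.

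Third, some details must not be overstated. The therapist is named only for the list review, so the 9 h is scheduled session time and not established therapist contact. The home tasks were reviewed afterwards, not supervised. Controls also received exercises, and the remark that all participants had the same list could mean all controls or both arms. The LE-MAL was given in all treatment sessions without an arm being stated; if controls had it too, the difference in time outside TT is smaller than 9 h.

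Finally, this is a small descriptive pilot, and restating an aim without a matching analysis would leave a new mismatch. That is right, and it is why the restated aim needs a between-arm estimate beside it. Small size argues against relying on a test. It does not argue against showing the difference with its interval.

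**Conclusion.** The point holds as a mismatch between aim, comparison and analysis. The effect of the combination is not identified by this design. The added effect of the TP package over TT plus handout is identified by the randomisation, but the plan as written does not estimate it. Within-arm change in TT+TP cannot stand in for either.

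The package carries 9 h of extra scheduled session time, 1.5 to 2.0 times the control schedule. That ratio measures the imbalance in time, not bias in any outcome.

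The conclusion assumes that Section 2 is complete as written, that its mean changes would be shown by arm, and that the schedule was delivered as described; delivered time is not reported.

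**What to change.** 1. **Aims.** Restate both as the added effect of the TP package as delivered, over the same TT schedule plus an exercise handout. Describe the package: 30 min of extra scheduled session time after each of 18 sessions, assigned and reviewed daily tasks, and home practice after treatment.
2. **Analysis.** For each outcome, report the between-arm difference in change from pre-treatment with a confidence interval at post-treatment, 3 months and 6 months. The text is in the past tense and reports allocation as done, so label any aim wording or estimate added after data collection as post hoc.
3. **Interpretation.** State that within-arm change, including change beyond an MCID or MDC, does not estimate the effect of the combination. Limit the conclusion to the package as a whole because session time was not matched.
4. **Reporting.** Give scheduled and, where recorded, delivered session hours by arm. Say whether the control exercise list and the per-session LE-MAL applied to one arm or both.

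No additional arm and no new data are needed beyond session records, where kept. The cost is a small amount of text and one set of estimates, a narrower claim, and intervals of roughly ±1 SD of change that will seldom settle the question.

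### Every outcome is judged only by change from pre-treatment against an MCID/MDC, with no TT+TP versus TT difference planned; the LE-MAL also needs a statement of which arm had it at sessions

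*Combined protocol and SAP*

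**What the plan says.** Section 1 (Study Protocol) describes a "parallel pilot randomized trial of a robotic treadmill gait protocol combined with behavior management strategies". One aim concerns "changes on walking speed, endurance, motor function and use of the affected LE". On the shared treatment it says: "All participants received the same TT, which consisted of 18 sessions distributed over 6 weeks". What differs is the add-on. "The intervention group (TT+TP) received the TT combined with the TP", while "The control group (TT) received the same treadmill training described above and also received a list of exercises" at session 1.

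Section 2 (Statistical Analysis Plan) names four primary outcomes (LE-MAL, BBS, 10MWT, 6MWT) and two secondary outcomes (5TSTS, FFABQ). They were measured before and after treatment and at 3 and 6 months, by a physical therapist who did not know the allocation. The final paragraph gives the analysis. Means and SDs are shown at each time point, and each later average is compared with the pre-treatment average. The difference is then held against an MCID or MDC, if the literature has one, to identify significant changes. The reason given is that the sample was too small for statistical analysis. The paragraph mentions neither arm.

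On the LE-MAL, Section 1 adds: "The use of the affected limb was assessed in all treatment sessions through the administration of the LE-MAL". This comes within the TP description, just before home practice is introduced as the final TP component. The control-arm paragraph that follows does not mention it.

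**The concern.** The randomised comparison is what this design has to offer. Both arms had identical treadmill training, so a change from pre-treatment contains whatever that training, the passage of time and trial participation produce in everyone. Section 1 itself says that treadmill training has improved walking speed and endurance during and immediately after intervention. Shared change is therefore realistic, at least for those outcomes.

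Under the planned reading, a TT+TP mean that passes an MCID could be reported as a significant change and credited to TP when the TT arm changed just as much. The reverse is also possible: a real TP effect could be missed because neither arm's mean reaches the threshold.

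The LE-MAL carries an extra question. It is the only outcome that the text ties to use of the affected limb, and TT+TP participants signed a contract whose purposes include to "increase use of the more-affected LE in daily tasks". If they alone also completed the LE-MAL at each session, the arms differ in exposure to the instrument as well as in treatment.

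**Working it through.** The plan states no SD, alpha, effect size or threshold value, so it has no precision or power figure to reproduce. Its counts agree: 3 modalities x 6 sessions = 18 sessions; 12 + 7 = 19 participants; 2:1 of 19 is 12.67 to 6.33, consistent with 12 and 7.

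**1. Comparisons planned.** 6 outcomes x 3 later visits = 18 comparisons with pre-treatment for each group averaged. Between-arm comparisons: 0.

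**2. What each comparison estimates.** Let c be change common to both arms, e the effect of adding TP, h the effect of the exercise handouts, and k any effect of repeated LE-MAL administration on the LE-MAL score (k = 0 for other outcomes). Assume additive effects. Take first the case where only TT had the handouts and only TT+TP had session LE-MAL:

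- TT+TP change = c + e + k
- TT change = c + h
- Pooled change = [12(c + e + k) + 7(c + h)]/19 = c + 0.632(e + k) + 0.368h
- Between-arm difference = e + k - h

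Only the last line is free of c. If both arms had the handouts, h cancels. If both had session LE-MAL and responded alike, k cancels.

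**3. How often common change alone passes the threshold.** Set e = k = 0, let M be the MCID or MDC, and use a normal approximation: P(TT+TP mean > M) = Phi((c - M) x sqrt(12)/SD). The values of c and SD are assumptions.

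- SD of change = M: for c = 0.5, 0.8, 1.0, 1.2 and 1.5 M, P = 0.04, 0.24, 0.50, 0.76 and 0.96.
- c = 0.8 M: P runs from 0.08 (SD 0.5 M) to 0.36 (SD 2 M).
- c = M: P = 0.50 whatever the SD. If h = 0 as well, TT+TP passes and TT does not with probability 0.5 x 0.5 = 0.25.

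These figures apply to any outcome with a published threshold. Because k is set to zero, they say nothing about session LE-MAL.

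**4. Precision available.** 95% CI half-widths in SDs of change, complete data:

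- TT+TP: t(0.975, 11)/sqrt(12) = 2.201/3.464 = 0.64
- TT: t(0.975, 6)/sqrt(7) = 2.447/2.646 = 0.92
- Between arms, common SD: t(0.975, 17) x sqrt(1/12 + 1/7) = 2.110 x 0.4756 = 1.00

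With the initial target of 24 split 16 v 8, the between-arm figure would have been 0.90. At an assumed two-sided alpha of 0.05, 12 v 7 gives 51% power for a true difference of 1.0 SD, and 80% power needs about 1.41 SD.

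**5. LE-MAL exposure.** TT+TP: 18 sessions + 4 assessments = 22 administrations. TT: 4 if the session LE-MAL belonged to TP, 22 if both arms had it. None is described between the end of treatment and the 3-month visit, so the follow-up visits are less exposed than the post-treatment visit.

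**The case against.** **This is a declared descriptive pilot.** The plan openly says that no statistical analysis was done because the sample was small. That is a fair reason for having no test. It does not prevent an estimate with an interval, and it does not justify calling a within-group change significant.

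**The aim can be read as the combined package.** The aim is worded as the effect of treadmill training with TP, so within-arm change might seem to answer it. But there is no untreated arm, so within-arm change does not isolate the effect of the combination either. What the randomisation can address is the add-on.

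**The threshold may not exist.** If the literature reports no MCID or MDC for an outcome, that outcome cannot be labelled and step 3 does not apply to it. This stands, and may apply to the LE-MAL. Section 1 also says it is unclear how well treadmill gains transfer to everyday situations, so common change in limb use could be small.

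**The between-arm difference is not a pure TP effect.** This stands. The control arm had an exercise handbook, and the sentence saying that all participants received the same exercise list could mean all controls or both arms. The contrast is TT+TP versus TT with handbook until that is settled.

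**A stronger reading is tempting for the LE-MAL.** A reader might infer that session-by-session administration biased this outcome in favour of TT+TP. The documents do not support that. No sentence restricts the session LE-MAL to TT+TP, and Figure 2 could not be seen. A shift in reporting presupposes a participant-reported scale; the text refers to a full description, but the material available gives only the name. The effect may be zero, and a real increase in use prompted by monitoring would be part of the TP effect. Blinded assessment, stated for the assessment visits only, would not by itself remove a participant's reporting shift, but that does not show one occurred.

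**Conclusion.** The point holds for all six outcomes. The plan's only criterion is change from pre-treatment against an MCID or MDC, which cannot separate the effect of adding TP from change common to both arms, whether averages are by arm or pooled. How often this misleads depends on unknown common change: from 0.04 to 0.96 across the assumed range with SD equal to the threshold, and 0.50 when common change equals the threshold. The between-arm difference removes common change, with a half-width of about 1.0 SD of change, assuming complete data and a common SD.

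The LE-MAL point is a matter of disclosure. The placement of the sentence suggests TT+TP only, but this is inference. If it is right, the between-arm difference keeps any effect of repeated administration in full, so the added contrast does not resolve it. The LE-MAL can remain a primary outcome.

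**What to change.** 1. For all primary and secondary outcomes, report change by arm with the number analysed. Add the between-arm difference in mean change with 95% CI at post-treatment, 3 months and 6 months, labelled post hoc. Doing this for the LE-MAL alone would be selective.
2. Base any statement about TP on that difference, described as TT+TP versus TT with the exercise handbook. State whether TT+TP also received the handouts.
3. Keep the MCID/MDC comparison as descriptive context, without the word *significant*, and say for which outcomes a threshold was found.
4. State which arm or arms had the LE-MAL at treatment sessions. If only TT+TP did, say that the difference still contains any effect of repeated administration, of unknown existence, size and direction.

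The cost is a few sentences and 6 x 3 = 18 table rows from measurements already planned. The intervals will be wide and results usually inconclusive. With 18 unadjusted intervals, 18 x 0.05 = 0.9 would be expected to exclude zero if there were no differences at all, so they should be read as estimates and not as tests.

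### Up to 24 unranked threshold checks can be called significant, with no rule for a claim and no between-arm comparison; the chance of a spurious crossing is unknown

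*Combined protocol and SAP*

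**What the plan says.** Section 2 (Statistical Analysis Plan) lists the outcomes without an order: "The primary outcomes were the Lower Extremity Motor Activity Log (LE-MAL), Berg Balance Scale (BBS), 10 Meter Walking Test (10MWT"), with the 6-minute walk test (6MWT) as the fourth. It then sets three visits against baseline: "The average scores at post-treatment, 3 months follow up and 6 month follow up visit were compared to the average scores obtained at pre-treatment". No visit is named as primary.

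The differences are held against an MCID or MDC for each outcome, where the literature reports one, in order to identify "significant changes since statistical analysis was not conducted due to the small sample size". The section gives no threshold values and no sources. It does not say how many outcomes or visits must reach the threshold before benefit is claimed, and it describes no comparison between arms.

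Participants were "randomly allocated using a 2:1 ratio to either TT+TP (N = 12) or TT group (N=7"). In Section 1 (Study Protocol) both arms receive the same treadmill training, so the randomised contrast concerns the TP. The second aim there is "long-term retention of improvement on these outcomes".

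**The concern.** The threshold rule stands in for hypothesis testing, and its output is called significant. A rule that attaches that label has an error rate even when none is stated. Here it is applied to several outcomes at several visits, and nothing fixes in advance which result, or how many, would support a conclusion.

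The second problem is what is compared. Change from pre-treatment within an arm mixes any effect of the TP with the effect of treadmill training, which both arms receive. The only way to reach a statement about the TP under this rule is to notice that TT+TP reached a threshold where TT did not. That pattern can arise when the arms truly change by the same amount, and 12 cells offer 12 chances to find it. The arms also differ in size (12 and 7), so their means carry different amounts of noise.

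**Working it through.** The plan states no alpha, power, SD or threshold, so it has no figure of its own to reproduce.

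**1. Count.** 4 outcomes × 3 visits = 12 cells per arm; × 2 arms = 24. This is an upper limit, because a threshold applies only where the literature reports one. The by-arm reading is an inference from the parallel two-arm design.

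**2. One cell, no true change.** Let c be the threshold divided by the SD of change. For an arm of size n, the chance that the mean change reaches the threshold in the direction of improvement is 1 − Φ(c√n), assuming normal changes and everyone assessed.

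| c | n = 12 | n = 7 |
|---|---|---|
| 0.3 | 14.9% | 21.4% |
| 0.5 | 4.2% | 9.3% |
| 0.8 | 0.3% | 1.7% |
| 1.0 | 0.03% | 0.4% |

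**3. At least one cell, no true change.** I assumed correlations of change scores of 0.3–0.5 between outcomes and 0.7–0.8 between visits (cross terms are the product) and simulated the 12 mean changes in each arm. Repeat runs agree to about one percentage point.

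| c | At least one of 24 cells |
|---|---|
| 0.3 | 83–90% |
| 0.5 | 52–61% |
| 0.8 | 13–15% |
| 1.0 | 3–4% |

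For c = 0.5 with 24 independent cells the figure would be 1 − (1 − 0.0416)^12 × (1 − 0.0929)^12 = 81%, so the assumed correlation lowers it materially. At the far end, suppose the criterion is an individual-level MDC at 95% and the SD of change is measurement error alone. Then c = 1.96 and the 24-cell figure is about 0.0001%, even with independence.

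**4. Equal true change in both arms.** What matters now is the distance between true change and threshold, not the size of the threshold. For one pre-named cell with true change at the threshold, each arm crosses half the time, so the chance that TT+TP crosses and TT does not is 0.5 × 0.5 = 25%. With true change 0.5 SD below it is 0.0416 × (1 − 0.0929) = 3.8%; with 0.5 SD above it is (1 − 0.0416) × 0.0929 = 8.9%. For at least one of 12 cells, under the correlations of step 3:

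| True change relative to threshold | TT+TP crosses, TT does not | TT crosses, TT+TP does not |
|---|---|---|
| 0.5 SD below | 20–25% | 37–46% |
| Equal | 73–82% | 73–82% |
| 0.5 SD above | 37–46% | 20–25% |

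The last column follows by symmetry: changing the sign of both arms' distance from the threshold swaps the two patterns.

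**5. Precision of the between-arm contrast.** The standard error is √(1/12 + 1/7) = 0.476 SD of change. With t(0.975, 17) = 2.110, the 95% half-width is 2.110 × 0.476 = 1.00 SD.

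**The case against.** The strongest reply is that this is a descriptive pilot with no alpha, no tests and no between-arm reading, so there is no error rate to control. Pilot status does lower the stakes. It does not close the gap, because Section 2 still uses the threshold to label changes significant, and Section 1 states its aim as the effect of the intervention.

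Three further points against the concern stand.

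- A reader might infer that at least one significant result is likely by chance. The documents do not support that. It holds for thresholds below roughly half an SD of change and fails at 0.8 SD or more, and they give neither the thresholds nor the SDs. The familiar 71% for 24 independent tests at 5% (1 − 0.95^24) does not apply either, since the plan runs no tests.
- A reader might infer a tilt towards TT+TP. The 73–82% is the worst case, and the reverse pattern is equally frequent there. With the true change below the threshold, the reverse pattern is the more frequent of the two.
- A reader might conclude that 6 months should become the sole primary visit, with a Holm adjustment or 98.75% intervals over four outcomes. Nothing in Section 1 ranks retention above the first aim. Section 2 is written in the past tense, so choosing a visit now could follow the data as easily as choosing an outcome could. At 12 versus 7 and a two-sided level of 0.0125, power is about 17% for a true difference of 0.8 SD and 28% for 1.0 SD.

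**Conclusion.** The structural gap holds: four unranked primary outcomes, three visits, an unspecified threshold that confers the word significant, no rule for a claim, and no comparison between the randomised arms. The number of checks is at most 12 per arm and 24 in all, on an inferred by-arm reading.

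How often this misleads cannot be fixed from the documents. With no true change, the chance of at least one crossing could be anywhere from negligible to about nine in ten, depending on threshold over SD. The firmer argument is the equal-change case, because a high threshold alone does not remove it. The search over 12 cells raises the misleading pattern from 25% for one pre-named cell to 73–82% when the true change sits at the threshold, and it remains at 20–46% half an SD away. These figures rest on assumed normality, correlations, equal SDs across arms and complete follow-up. They show that selective reading is possible, not that it occurred.

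**What to change.** In Section 2:

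- For the four primary outcomes at all three visits, report the between-arm difference in change from pre-treatment with a confidence interval. Base any statement about the TP on these differences, not on one arm reaching an MCID or MDC.
- Report all 12 outcome-by-visit cells for both arms.
- State each threshold and its source, and say where none is published.
- Replace the label of significant change with a plain statement that the mean change reached the MCID or MDC.
- State that the results are exploratory and that no single outcome-visit crossing supports a claim of benefit.
- Do not pick one primary outcome or visit now unless it can be shown that results had not been seen. If a familywise claim is wanted, adjust over all the contrasts used for it.

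The cost is a few lines of text and a small amount of analysis, with no new data. The downside is wide intervals (about ±1.00 SD of change per contrast at 95%), so the results will look less favourable than a list of crossed thresholds.
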